		Intention for the patient to be screened	DECAD Created	3-items total. Two on a 5-point scale to assess propensity to get screened. One to ask how many more mammograms they think the patient will get.	Yes vs. those who are unsure vs. No screening; We will look at the scores continuously and categorize scores as 1-2(no), 3 (unsure), or 4-5 (yes).	T1 T3	Caregiver and Patient reported

		Breast Cancer and Alzheimer's disease Knowledge	DECAD Created	16-items (6 multiple choice and 10 true/false); 13 were adapted from other studies and 3 were developed based on the decision aid.	Sum of correct answers	T1 T3	Caregiver reported
		Burden of screening on the patient	DECAD Created	Review patient's EMR for additional diagnostic procedures due to mammogram follow-up; false-positive results, identification of an abnormality on screening exam but further work-up declined, identification of a clinically unimportant cancer; documentation of depressive symptoms, anxiety, or pain related to the experience of getting a mammogram and not a general measure to be assessed independent of that event	Yes or no Characterization if yes	T4 T5 (quarterly for DSBM )	Pt EMR review;
		Burden of screening on the caregiver	DECAD Created	5 items on a 5-point Likert scale. Assess perceptions about the burden of mammography for the patient & Semi-structured questions about patient's mammogram experience and perceived burden of screening.	Sum of scores	T4	Caregiver reported
	Values, Attitudes, Norms, and Experiences		DECAD created	15 items total. 5 items on a 10 point scale re: values; 3 items on a 7 point scale on attitudes; and 3 items on a 5 point scale re: perceived norms; and 4-items on a 5 point scale re: experience with mammograms	descriptive	T1 T3	Caregiver and Patient reported
		Health literacy		A 4-item health literacy assessment with values of 0-5 based on possible responses to each of the questions. 	Higher scores being higher health literacy.	T1	Caregiver reported
		Numeracy		A 3-item assessment of numeracy skills	Higher scores being higher health literacy.	T1	Caregiver reported
	Mammogram discussion with the Patient's provider			8-items that assess if a discussion about mammograms took place and the content of those discussions.	Descriptive	T3	

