# DECAD Study Timeline

## Step 2: Enrollment

- Following eligibility determination and the informed consent process (which includes HIPAA release form), and baseline assessment the dyads will be randomly assigned in 1:1 ratio to one of two groups: mammogram decision aid or home safety guide, stratified by site.
- Decision aid or home safety guide will be mailed to both the patient and the caregiver immediately after randomization but at least 1 week before the index visit.
- Date of the patient's next PCP visit will be obtained via caregiver report at the baseline interview and via EMR review at the time of enrollment.
- For all dyads, the Research Assistant will meet them in person or by phone 0-2 days before the index visit to standardize the process by which all dyads review the decision aid. The pre-index visit assessment (T2) will occur in-person or by phone 30 minutes-2 days before the index visit either at the patient's house, at the caregiver's house, at the provider office or at a location of the dyads choice. Observational data only is collected at this assessment. The RAs will not discuss the content of the decision aid at that time; they will simply ensure that they have read it or have had it read to them before the index visit. We will record if the RA is asked to read the DA to either member of the dyad. If

the dyad has any questions about the content of the decision aid, the RA will encourage them to ask the patient's provider any questions. The phone option script will provide prompts to ensure review of the decision aid during the phone conversation

- If the date of the patient's index visit is not known or not documented in the EMR, the RA will follow the study tracking process to obtain the patient's index visit appointment date. This includes a 2x per month phone call to the caregiver and EMR review (if accessible).
- If the index PCP visit does not occur within approximately six months of the baseline, another provider visit may be substituted with PI permission.
- The post- index visit (T3) will occur in-person or via phone 0-5 days after the index visit.

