#### Step 3: Secondary Aim

- A binary indicator variable for receipt of mammograms within 15 months and within 24 months from the intervention date will be used as a secondary outcome variable.
- A logistic model with group (decision aid or control) as the independent variable will be used adjusting for recruitment sites (e.g., EH, IUH and IADC) and other potential baseline covariates found to be different in univariate comparisons.

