## **STATISTICAL POWER**

Sample size for the proposed trial is calculated using our pilot data that showed effect sizes of 0.28 on Decision Conflict Scale (DCS) score and 0.34 for self-efficacy scores. To detect effect size of 0.28 or greater on DCS scores between the two groups, we will need to have 202 patient/caregiver dyads per group to complete both baseline and follow-up with 80.2% power using two sample *t*-test at 0.05 level. Allowing 5% missing data at follow-up, we will need to enroll 213 patient/caregiver dyads per group (total 426 dyad baselines). With our planned sample size, we will have 92.6% to detect effect size of 0.34 or greater on changes in self-efficacy scores between the two groups.

The pilot showed the mean DCS were similar between the two groups, the control group had a large SD which should come down with large sample size. Table 4.

Table 4. Baseline DCS scores						
Group	N	Mean	Std Dev	Std Err	Minimum	Maximum
Control	8	26.8375	22.6769	8.0175	0	69.0000
Decision support	9	26.4444	16.4249	5.4750	0	45.0000

Change in DCS from baseline to follow-up: DA group had greater decrease in DCS than controls. The current effect size is about 0.55. Table 5.

Table 5. Change in DCS scores from baseline to follow-up, by group						
Group	N	Mean	Std Dev	Std Err	Minimum	Maximum
Control	8	5.2000	8.8073	3.1139	-6.0000	21.0000
Decision support	9	9.7778	7.8705	2.6235	0	20.0000
Diff (1-2)		-4.5778	8.3208	4.0432		

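### The mammogram-receipt models do not pre-specify T1 screening intention, and their imbalance-based covariate rule gives up some precision that is free to take

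*Combined protocol and SAP*

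**What the plan says.** **Receipt model.** Statistical Plan, Step 3 (Secondary Aim), defines receipt as a yes/no indicator within 15 and within 24 months and states: "A logistic model with group (decision aid or control) as the independent variable will be used adjusting for recruitment sites". The same sentence adds other potential baseline covariates, but only those that univariate comparisons show to differ. Step 3 gives no threshold for differing and no list of candidates. Step 2 does require a significant difference for the primary outcome. Step 1 names only demographic characteristics for the between-arm comparison.

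**Screening intention.** Table 3 lists a three-item measure of intention for the patient to be screened, at T1 and T3, from both caregiver and patient: "Two on a 5-point scale to assess propensity to get screened", plus one item on how many more mammograms are expected. Scores are to be looked at continuously and also grouped as no, unsure or yes.

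**Timing.** Step 2: Enrollment puts the baseline assessment before dyads are "randomly assigned in 1:1 ratio to one of two groups", stratified by site. T1 intention is therefore a legitimate covariate.

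**Other analysis steps.** The moderators in Step 4 do not include intention. Step 5 adds predictors of missingness to the ANCOVA models only, not to the logistic models.

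**Power.** The Statistical Power section covers decisional conflict and self-efficacy. It gives neither power nor an assumed rate for mammogram receipt.

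**The concern.** A receipt outcome has no usable yes/no baseline here. Table 1 requires a mammogram in the past five years and excludes one in the past six months, so prior receipt is the same for everyone. Intention is the T1 measure in Table 3 that asks most directly about the outcome, and under Step 3 it enters the model only if the arms happen to differ on it.

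Two things follow. First, any precision available from a prognostic baseline is mostly forgone, because at the 0.05 level a randomised variable differs significantly in about 5% of trials, whatever its relation to the outcome. Second, the covariate list for the Secondary Aim is known only after the baseline data are compared. Receipt is the whole of that aim and has no stated power, so precision from data already planned is worth having.

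**Working it through.** **1. The plan's own figures.** Two-sided two-sample t-test, alpha 0.05, noncentrality d × √(n/2), with n from "we will need to have 202 patient/caregiver dyads per group":

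- d = 0.28: 0.28 × √101 = 2.81, power 80.16% (plan: 80.2%).
- d = 0.34: 0.34 × √101 = 3.42, power 92.63% (plan: "we will have 92.6% to detect effect size of 0.34 or greater").
- Allowance for missing data: 202 / 0.95 = 212.6, rounded up to 213 (plan: "Allowing 5% missing data at follow-up, we will need to enroll 213 patient/caregiver dyads per group").

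All reproduce, and none is in dispute. They do not concern receipt.

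**2. What 202 per arm can detect on receipt without intention.** The control rate is an assumption. The smallest absolute reduction with 80% power is 11.9 points at a control rate of 30%, 13.2 at 40%, 13.8 at 50% and 13.9 at 60%.

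For the working scenario of 50% vs 37%:

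- Pooled rate 0.435; null SE = √(2 × 0.435 × 0.565 / 202) = 0.0493.
- Alternative SE = √((0.25 + 0.2331) / 202) = 0.0489.
- z = (0.13 − 1.96 × 0.0493) / 0.0489 = 0.68, power about 75%.

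**3. Gain from fixing intention in the model.** These are simulated logistic models at two-sided 0.05, fitted with and without the score. Every rate, split and association is an assumption. Splits are no/unsure/yes, and the odds ratio (OR) is for receipt, yes vs no.

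| Setting (50% vs 37% receipt) | Association | Gain in power, points |
|---|---|---|
| 202 per arm, 20/20/60 | OR 3 to 8 | about 1 to 7 |
| 202 per arm, 5/20/75 | OR 3 to 8 | about 1 to 2 |
| 213 per arm, 20/20/60 | OR 3 | 1.7 (77.6% to 79.3%) |
| 213 per arm, 20/20/60 | OR 5 | 3.5 (76.7% to 80.2%) |
| 213 per arm, 20/20/60 | OR 8 | 4.5 (78.8% to 83.3%) |
| 213 per arm, 5/20/75 | OR 3, 5, 8 | about 1.5, 2.5, 3 |
| 202 per arm, five-level score | correlation 0 | none (74.5% vs 74.4%) |

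The runs at 213 per arm and with the five-level score used 4,000 trials per scenario. The Monte Carlo standard error of one power figure is then √(0.75 × 0.25 / 4000) = 0.7 points. Only differences within a row should be read, since both models are fitted to the same simulated data.

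**4. What the conditional rule recovers.** At 202 per arm and the same odds ratios, entering intention only when the arms differ on it gained under 1 point.

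**5. What adjustment does to the reported effect.** The unadjusted odds ratio is (0.37/0.63) / (0.50/0.50) = 0.587. With the five-level score in the model, the same 13-point difference corresponds to a conditional odds ratio of 0.570, 0.528 or 0.476 as the association strengthens (correlation about 0.24, 0.42, 0.54). The plan must therefore say which effect it reports.

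**The case against.** The strongest reply is that nothing here is wrong. Under 1:1 randomisation the site-adjusted comparison is valid, no section promises adjustment for intention, and no stated figure changes. That stands. A reader might infer that omitting intention biases the receipt result; the documents do not support this.

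A second reply is that the prognostic strength of intention has no source in the documents. The intervention aims to change the decision after T1, and follow-up runs to 24 months in women with dementia, so baseline intention may lose its predictive value. Table 1 also excludes patients and caregivers who have decided to stop mammograms, which thins the low end of the score. This stands too, and it is why the lower gains are the likelier ones. With a five-level score and correlations of about 0.35 to 0.54 with receipt, simulated gains run from about 5 to 12 points. A reader might take those as the expected gain, but nothing in the documents supports so strong an association.

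Third, intention is not the only candidate. Time since the last mammogram, and the T1 values, attitudes, norms and experience items, could also serve. Calling intention the closest baseline is a judgement. Nor is it barred: the conditional clause could admit it. That clause selects on imbalance, though, and step 4 of the working shows how little it recovers.

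Fourth, adding one covariate while keeping the selection rule would leave the model unsettled. This is right, and the fix therefore replaces the rule.

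**Conclusion.** The point holds as a free improvement in precision and pre-specification. Step 3 fixes only group and site and chooses everything else by between-arm difference, so T1 intention, planned for both members of each dyad before randomisation, is not pre-specified for the outcome it bears on most directly.

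The gain cannot be settled from the documents. Assuming 202 per arm and 50% vs 37% receipt, it runs from nil with no association to about 1 to 7 power points at odds ratios of 3 to 8. It falls to about 1 to 2 points under the narrower 5/20/75 split that the eligibility rules make plausible. No loss of note appeared when intention was not prognostic. The validity of the trial, its sample size and its primary analysis are unaffected.

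**What to change.** In Step 3, for both the 15- and 24-month models:

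1. Delete the rule that admits covariates according to between-arm differences. Name the covariates instead: recruitment site and T1 caregiver screening intention.
2. Define the intention score as the mean of the two 5-point items, entered as continuous. Table 3 does not define such a mean, so the definition must be written down.
3. State a simple rule for missing scores that does not use treatment arm, for example the answered item if only one is present, otherwise the mean over both arms combined. Using the caregiver score avoids dependence on patient self-report.
4. Report the arm effect as a standardised (marginal) risk difference: predict each patient's probability of receipt under each arm from the fitted model, average over all patients, and subtract. The covariate then does not change the quantity being estimated.

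The cost is a few sentences in the plan, settled before receipt is compared by arm. The data are already scheduled at T1, and neither the 426 dyads nor the conduct of the trial changes.

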#### Step 4: Exploratory Aim

- Once we have tested our hypothesis for the main effects, we will also perform hypothesis-generating exploratory analyses to examine effects in sub-groups of patients and caregivers.
- Hypothesized sub-group analyses will be used for both the primary and secondary outcomes examining the moderating effect of patients' and caregivers' characteristics on decision aid impact.
- The following patient variables will be included in sub-group analyses: age, level of cognitive impairment, number of co-morbidities, and their role in mammography decisions.
- The following caregiver variables will be included in sub-group analyses: relationship to the patient, level of education, health literacy, and perceived burden of mammography for the patient and for them.
- We will include each of these variables in the ANCOVA models for the primary outcome, in the logistic models for the secondary outcome and test for interactions between these variables and intervention group adjusting for recruitment sites and other potential baseline covariates. Significant interaction between a patient/caregiver characteristic variable and group would indicate different intervention effects in the dyad subgroups defined by the variable.

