Primary outcome	Feel Informed Values clarification	Decisional Conflict	Decision Conflict Scale	16-items on a 1-5 Likert scale. Measures uncertainty around a decision, whether	Scores range 0-100; Lower	T1 T3	Caregiver reported

				one feels informed, clear about their personal values, and supported in their decision-making.	scores indicate less conflict.		
Secondary outcomes	Belief in ability to make and participate in shared decision making	Decision-making self-efficacy	Decision Self-Efficacy Scale (DSE)	11-items on a 5-point Likert scale. Measures of self-confidence or belief in one's ability to make decisions	Low, medium, high decision self-efficacy. Scores range 0-100	T1 T3	Caregiver reported
		Receipt of screening	DECAD Created	Review primary care notes, radiology reports, and documentation on screening/preventive care; caregiver report	Yes or no determination	T4 T5	Pt EMR; Caregiver reported
	Involvement in the decision	Caregiver role in decision-making	Adapted from the Control Preferences Scale	4-items to assess preferences for and involvement in making decisions on their own or sharing responsibility with the pt or doctor.	Active vs. passive/shared with doctor (since aim of decision aids is to help dyads be more active in decision-making)	T3	Caregiver reported
		Patient role in decision-making	Adapted from the Control Preferences Scale	2-items to assess involvement in making decisions on their own or sharing responsibility with their family or doctor.	Active vs. passive/shared with doctor (since aim of decision aids is to help dyads be more active in decision-making)	T3	Patient reported
Other measures		Socio-demographics	DECAD Created	32 item questionnaire to measure items such as relationship to the patient, frequency and type of contact with the patient, geographic distance from the patient, education level, annual income, self-reported health status, etc.	Co-variates	T1	Caregiver reported
	Does severity of the patient's cog and functional impairment impact caregiver decision making	Severity of patient's cognitive impairment	Dementia Severity Rating Scale (DSRS)	12-item questionnaire for caregivers to assess severity of AD in 12 major functional and cognitive domains.	Score ranges from 0 (mild) to 54 (severe).	T1	Caregiver reported
			Caregiver Appraisal of Function and Upset (CAFU)	15-item questionnaire for caregivers to measure ADLs and iADLs impairment and how much those impairments upset or burden the caregiver		T1	Caregiver reported

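### Step 4 reads interactions with patient role and caregiver-perceived burden as different intervention effects, but Table 3 lists both only after randomisation (T3 and T4)

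*Combined protocol and SAP*

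**What the plan says.** Step 4 of the Statistical Plan describes "hypothesis-generating exploratory analyses to examine effects in sub-groups of patients and caregivers". It lists four patient moderators, ending with "number of co-morbidities, and their role in mammography decisions", and four caregiver moderators, ending with "health literacy, and perceived burden of mammography for the patient and for them". Each is to be entered in the ANCOVA or logistic model and tested for interaction with group; the plan states that "Hypothesized sub-group analyses will be used for both the primary and secondary outcomes". It then gives a rule for reading the result: a significant interaction "would indicate different intervention effects in the dyad subgroups defined by the variable".

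The timing of the two variables comes from Table 3:

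- **Patient role in decision-making** is listed at T3 only, under secondary outcomes. Its scoring note gives the reason for the coding: "since aim of decision aids is to help dyads be more active in decision-making".
- **Burden of screening on the caregiver** is listed at T4 only. Its description begins "Assess perceptions about the burden of mammography for the patient", which closely matches Step 4's wording.

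Under Step 2 (Enrollment), dyads are randomised after the baseline (T1) assessment. T3 falls 0 to 5 days after the index visit, and T4 is the 15-month follow-up.

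**The concern.** An interaction between group and a baseline variable compares randomised groups within each level of that variable. If the variable is recorded after randomisation and the intervention can move it, the decision-aid and control dyads within a level need not be alike, even though the arms were alike at the start. A difference between levels may then reflect who ended up in them.

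For role, the plan itself expects movement, since it treats role as something decision aids change. For burden, the ordering is worse. T4 comes after the T3 primary outcome and coincides with the end of the 15-month mammogram window, so reported burden may be a consequence of being screened, which is the outcome in that model.

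At stake is a published statement that the aid works differently by patient role or by perceived burden when the subgroups were shaped by the aid or by screening.

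**Working it through.** **Timing.** The Step 4 moderators against Table 3:

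| Moderator | Where listed | Before randomisation? |
|---|---|---|
| Age | Pre-randomisation characteristic | Yes |
| Cognitive impairment | Dementia Severity Rating Scale, T1 | Yes |
| Co-morbidities | No Table 3 row | Not stated |
| Patient role | T3 only | No |
| Relationship, education | Socio-demographics, T1 | Yes |
| Health literacy | T1 | Yes |
| Perceived burden | T4 only | No |

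**Count.** Step 3 defines "receipt of mammograms within 15 months and within 24 months from the intervention date", so there are three outcomes with the Decisional Conflict Scale (DCS). Affected tests: 2 moderators × 3 outcomes = 6, of 8 × 3 = 24. The count rises if burden is two variables or self-efficacy is included.

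**The plan's own figure.** The Statistical Power section gives 202 completing dyads per group and 80.2% power at effect size 0.28. The noncentral t gives 80.16%, and 202 / 0.95 = 212.6, rounded up to 213. These figures are not in dispute; 202 is used below.

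Everything that follows is illustrative. The inputs are assumptions, there is no true treatment effect, and tests are at the 5% level.

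**Role and DCS.** Let L be standard normal in each arm, with role active if L > c. The outcome is r × L plus noise, with unit variance. Suppose active role goes from 50% (control) to 65% (aid).

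- Mean of L if active: 0.399 / 0.50 = 0.798 (control); 0.370 / 0.65 = 0.570 (aid). Difference −0.228.
- Mean of L if not active: −0.798 (control); −0.370 / 0.35 = −1.058 (aid). Difference −0.260.
- Spurious effect within a subgroup = r × difference. Spurious interaction = r × (0.260 − 0.228) = r × 0.032.

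| r, both arms | Shift, active (SD) | Shift, not active (SD) | Interaction (SD) | Rejection |
|---|---|---|---|---|
| 0.1 | 0.023 | 0.026 | 0.003 | 4.9% |
| 0.3 | 0.068 | 0.078 | 0.010 | 5.1% |
| 0.5 | 0.114 | 0.130 | 0.016 | 5.2% |

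The rejection rates come from 20,000 simulated trials at 202 per arm. So a shift in role alone biases the subgroup estimates but hardly touches the interaction test. The test is misled if the aid also changes the correlation. Control versus aid: 0.1 vs 0.15 gives 0.08 SD and 6.7%; 0.1 vs 0.2 gives 0.17 SD and 13.3%; 0.3 vs 0.4 gives 0.17 SD and 14.1%; 0.3 vs 0.5 gives 0.34 SD and 40.6%. Nothing in the documents suggests such a change.

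**Burden and 15-month mammogram.** Assume the same mammogram rate in both arms, and high burden in 30% of dyads except unscreened decision-aid dyads, where it is h. By Bayes' rule the mammogram rate cancels:

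- Odds ratio, high burden = 0.30 / h. Odds ratio, low burden = 0.70 / (1 − h).
- h = 0.40: 0.75 and 1.17, ratio 0.64.
- h = 0.50: 0.60 and 1.40, ratio 0.43.

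The true ratio is 1. Rejection by the Wald interaction test, over mammogram rates of 30%, 50% and 70% (400,000 runs each):

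| Dyads per arm (assumed) | h = 0.40 | h = 0.50 |
|---|---|---|
| 202 | 15.5–17.9% | 43.8–51.5% |
| 150 | 12.7–14.4% | 34.2–40.3% |
| 120 | 11.1–12.6% | 28.4–33.6% |

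If burden rises to 40% equally in screened and unscreened decision-aid dyads, rejection stays at 5.0–5.1%.

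Role against mammogram receipt, burden against DCS, and burden against 24-month receipt were not modelled.

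**The case against.** The timing is inferred. Step 4 names no instrument or visit, the plan points to both Table 3 and Figure 1 for timing, and Figure 1 is not available here. Table 3 is not exhaustive for Step 4 either, since co-morbidities has no row. The sponsor might have meant T1 items, such as those on experience with mammograms in the Values, Attitudes, Norms, and Experiences row. This stands as a caveat. However, nothing labels those items as role or burden, and the only rows that match by name are at T3 and T4.

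The numerical harm is also conditional. For role, the interaction test that Step 4 relies on keeps its 5% level in the main scenario. For burden, a false interaction needs burden to rise differently in screened and unscreened decision-aid dyads, and the number with T4 data is not given. All this is correct, and the rejection rates are illustrations rather than predictions.

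Finally, the analyses are labelled hypothesis-generating and follow the main tests, and the exploratory hypothesis names only cognitive severity, co-morbidities and age. That limits the weight of the point, but it does not make the stated reading rule correct. Softening that rule to an association would meet part of the objection without dropping the two moderators, but it would leave the visit unstated and the tests still presented as moderation.

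**Conclusion.** The concern holds, as a minor point. On the timing in Table 3, two of the eight moderators are measured after randomisation, one of them a secondary outcome and the other recorded at 15 months. For these two, Step 4's rule does not follow: a significant interaction would not by itself show that the aid works differently. At least six of 24 exploratory tests are affected.

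Under the assumed inputs, the false-positive rate runs from about 5% (role shifted only, or burden raised equally) to roughly 40–50% under the stronger assumptions at 202 per arm. Which of these applies cannot be known from the documents. The sample size, the primary and secondary analyses and the named exploratory hypotheses are unchanged.

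**What to change.** State the instrument and visit for every Step 4 moderator, and restrict the effect-modification tests to variables measured at T1. Report patient role as the secondary outcome it already is, and caregiver-perceived burden descriptively by arm. If any tabulation by T3 role or T4 burden is kept, label it descriptive and draw no effect-modification claim from it. Use a T1 substitute only if its content really measures role or burden; if the sponsor intended such items, naming them settles the point.

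The cost is a change of SAP wording. No new data are needed and the sample size does not change. Two moderators, and so at least six exploratory interaction tests, are dropped or relabelled.
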